### **A6-1.2.8 Pancreatic Events**

The differential diagnosis of acute abdominal pain should include pancreatitis. Appropriate workup should include an evaluation for ductal obstruction, as well as serum amylase and lipase tests. Management guidelines for pancreatic events, including pancreatitis, are provided in [Table A6-5](#).

### **A6-1.2.9 Dermatologic Events**

The majority of cases of rash reported with the use of atezolizumab were mild in severity and self-limiting, with or without pruritus. Although uncommon, cases of severe cutaneous adverse reactions such as Stevens-Johnson Syndrome and toxic epidermal necrolysis have been reported with atezolizumab. A dermatologist should evaluate persistent and/or severe rash or pruritus. A biopsy should be considered unless contraindicated. Management guidelines for dermatologic events are provided in [Table A6-5](#).

### **A6-1.2.10 Neurologic Disorders**

Participants may present with signs and symptoms of sensory and/or motor neuropathy. Diagnostic workup is essential for an accurate characterization to differentiate between alternative etiologies. Management guidelines for neurologic disorders are provided in [Table A6-5](#).

## Appendix 6: Safety Plan: Management of Identified and Potential Risks

---

### **A6-1.2.11 Immune-Mediated Meningoencephalitis**

Immune-mediated meningoencephalitis should be suspected in any participant presenting with signs or symptoms suggestive of meningitis or encephalitis, including, but not limited to, headache, neck pain, confusion, seizure, motor or sensory dysfunction, and altered or depressed level of consciousness. Encephalopathy from metabolic or electrolyte imbalances needs to be distinguished from potential meningoencephalitis resulting from infection (bacterial, viral, or fungal) or progression of malignancy, or secondary to a paraneoplastic process.

All participants being considered for meningoencephalitis should be urgently evaluated with a CT scan and/or MRI scan of the brain to evaluate for metastasis, inflammation, or edema. If deemed safe by the treating physician, a lumbar puncture should be performed, and a neurologist should be consulted.

Participants with signs and symptoms of meningoencephalitis, in the absence of an identified alternate etiology, should be treated according to the guidelines in [Table A6-5](#).

### **A6-1.2.12 Renal Events**

Eligible participants must have adequate renal function. Renal function, including serum creatinine, should be monitored throughout study treatment. Participants with abnormal renal function should be evaluated and treated for other more common etiologies (including prerenal and postrenal causes, and concomitant medications such as non-steroidal anti-inflammatory drugs). Refer the participant to a renal specialist if clinically indicated. A renal biopsy may be required to enable a definitive diagnosis and appropriate treatment.

Participants with signs and symptoms of nephritis, in the absence of an identified alternate etiology, should be treated according to the guidelines in [Table A6-5](#).

### **A6-1.2.13 Immune-Mediated Myositis**

Myositis or inflammatory myopathies are a group of disorders sharing the common feature of inflammatory muscle injury; dermatomyositis and polymyositis are among the most common disorders. Initial diagnosis is based on clinical (muscle weakness, muscle pain, skin rash in dermatomyositis), biochemical (serum creatine kinase increase), and imaging (electromyography/MRI) features, and is confirmed with a muscle biopsy. Patients with possible myositis should be referred to a rheumatologist or neurologist. Patients with possible myositis should be monitored for signs of myocarditis.

Participants with signs and symptoms of myositis, in the absence of an identified alternate etiology, should be treated according to the guidelines in [Table A6-5](#).

## Appendix 6: Safety Plan: Management of Identified and Potential Risks

---

### **A6-1.2.14 Hemophagocytic Lymphohistiocytosis**

Immune-mediated reactions may involve any organ system and may lead to HLH and macrophage activation syndrome (MAS).

Clinical and laboratory features of severe CRS overlap with HLH, and HLH should be considered when CRS presentation is atypical or prolonged.

Participants with suspected HLH should be diagnosed according to published criteria by McClain and Eckstein (2014). A participant should be classified as having HLH if 5 of the following 8 criteria are met:

- Fever  $\geq 38.5^{\circ}\text{C}$
- Splenomegaly
- Peripheral blood cytopenia consisting of at least 2 of the following:
  - Hemoglobin  $< 90 \text{ g/L}$  (9 g/dL)
  - Platelet count  $< 100 \times 10^9/\text{L}$  (100,000/ $\mu\text{L}$ )
  - ANC  $< 1.0 \times 10^9/\text{L}$  (1000/ $\mu\text{L}$ )
- Fasting triglycerides  $> 2.992 \text{ mmol/L}$  (265 mg/dL) and/or fibrinogen  $< 1.5 \text{ g/L}$  (150 mg/dL)
- Hemophagocytosis in bone marrow, spleen, lymph node, or liver
- Low or absent natural killer cell activity
- Ferritin  $> 500 \text{ mg/L}$  (500 ng/mL)
- Soluble IL-2 receptor (soluble CD25) elevated  $\geq 2$  standard deviations above age-adjusted laboratory-specific norms

Participants with suspected MAS should be diagnosed according to published criteria for systemic juvenile idiopathic arthritis by Ravelli et al. (2016). A febrile participant should be classified as having MAS if the following criteria are met:

- Ferritin  $> 684 \text{ mg/L}$  (684 ng/mL)
- At least 2 of the following:
  - Platelet count  $\leq 181 \times 10^9/\text{L}$  (181,000/ $\mu\text{L}$ )
  - AST  $\geq 48 \text{ U/L}$
  - Triglycerides  $> 1.761 \text{ mmol/L}$  (156 mg/dL)
  - Fibrinogen  $\leq 3.6 \text{ g/L}$  (360 mg/dL)

Participants with suspected HLH or MAS should be treated according to the guidelines in [Table A6-5](#).

## Appendix 6: Safety Plan: Management of Identified and Potential Risks

---

### **A6–1.3 RISKS ASSOCIATED WITH COMBINATION USE OF LURBINECTEDIN AND ATEZOLIZUMAB**

Lurbinectedin and atezolizumab have anticipated molecule-specific safety profiles based on their mechanism of action and adverse events that may overlap.

- The most frequent adverse events specific to each drug include hematological toxicities for lurbinectedin and immune-mediated adverse events for atezolizumab.
- Atezolizumab treatment is not predicted to further impact hematological abnormalities commonly observed with lurbinectedin treatment in the proposed Phase III Study GO43104. However, given the risk factors of this participant population, primary G-CSF prophylaxis and monitoring via hematological tests have been implemented as risk mitigation measures (see Section 6.1.3 for more information).
- Immune-mediated adverse events observed with atezolizumab treatment are well-known, manageable and/or reversible. The Sponsor does not predict lurbinectedin treatment to impact immune-mediated adverse events.

Overlapping adverse events may include hepatotoxic, gastrointestinal, muscular and renal events, as well as signs and symptoms such as fatigue and decreased appetite that may be related to multiple system organ class events. For the management of such potentially overlapping adverse events in participants treated with lurbinectedin in combination with atezolizumab, adverse events should be managed according to the recommendations in Section A6–2.3.1 (lurbinectedin) and Section A6–2.3.2 (atezolizumab), applied to the component of the study treatment judged to be the primary cause.

The attribution of causality for certain adverse events may be uncertain when the drugs are administrated as a combination treatment and warrants diagnostic investigation. If causality for an adverse event with study treatment cannot be adequately determined, conservative management recommendations should be followed to include dose modification/interruption of both agents.

At present, considering the different mechanisms of action of lurbinectedin and atezolizumab, the initial safety profile from Study ML40908 (lurbinectedin+atezolizumab), and data from molecules with similar mechanisms of action (Chawla et al. 2018; Gordon et al. 2018), overlapping toxicities are expected to be limited and no exacerbations are anticipated.

## Appendix 6: Safety Plan: Management of Identified and Potential Risks

---

### A6-1.4 ETOPOSIDE

The risk of overlapping toxicities between atezolizumab, carboplatin, and etoposide is thought to be minimal. Etoposide is known to cause bone marrow suppression including myelosuppression, anemia, thrombocytopenia, gastrointestinal symptoms (e.g., nausea, vomiting, diarrhea), hepatotoxicity, and alopecia. Etoposide-based chemotherapy is considered to be moderately emetogenic. Etoposide carries a risk of secondary hematologic malignancy. Participants will be monitored for etoposide-related adverse events.

For more details regarding the safety profile of etoposide, refer to the etoposide prescribing information.

### A6-1.5 CARBOPLATIN

The risk of overlapping toxicities between atezolizumab, carboplatin, and etoposide is thought to be minimal. Carboplatin is known to cause bone marrow suppression including myelosuppression, anemia, and thrombocytopenia. Carboplatin-based chemotherapy is considered to be moderately emetogenic. Participants will be monitored for carboplatin-related adverse events.

For more details regarding the safety profile of carboplatin, refer to the carboplatin prescribing information.

## A6-2 MANAGEMENT OF PARTICIPANTS WHO EXPERIENCE ADVERSE EVENTS

### A6-2.1 DOSE MODIFICATIONS

#### Lurbinectedin

Dose modifications for lurbinectedin are as follows:

- Up to 2 individual lurbinectedin dose reductions are allowed ([Table A6-1](#)). Once the dose has been reduced for an individual participant, it must not be re-escalated again under any circumstances. Participants who continue to experience treatment-related toxicity and/or frequent dose delays after permitted dose reductions must discontinue treatment with lurbinectedin. They can continue receiving the study medication if objective clinical benefit is adequately documented by the investigator, and upon agreement with the Sponsor. If the participant receives a lurbinectedin dose of 2 mg/m^2 and experiences a toxicity that would warrant a lurbinectedin dose reduction, treatment with lurbinectedin must be permanently discontinued.

## Appendix 6: Safety Plan: Management of Identified and Potential Risks

---

- Participants may continue lorbinecetin at a reduced dose after they have adequately recovered from any of the following:
  - Grade  $\geq 3$  treatment-related non-hematological toxicity
  - Grade 4 thrombocytopenia or Grade 3 thrombocytopenia concomitantly with Grade  $\geq 3$  bleeding
  - Grade 4 neutropenia, any Grade febrile neutropenia or neutropenia associated with infection/sepsis
  - Frequent or prolonged ( $> 1$  week) dose delay due to treatment-related adverse events

Refer to [Table A6-2](#) for a list of criteria for treatment continuation.

Exceptions: patients experiencing treatment-related Grade  $\geq 3$  nausea and/or vomiting not optimally treated, Grade 3 asthenia lasting  $\leq 3$  days, Grade 3 diarrhea lasting  $\leq 2$  days or not optimally treated, Grade 3 transient ALT/AST elevations which are rapidly reversible and not leading to subsequent delays, and non-clinically relevant biochemical abnormalities, may continue treatment at the same prior dose without any dose reduction being applied, provided optimal concomitant treatment is given for the applicable toxicity.

Participants who experience Grade 3 or Grade 4 hypersensitivity reactions or Grade 3 or Grade 4 rhabdomyolysis will be discontinued from lorbinecetin.

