### **A6–2.4 MANAGEMENT GUIDELINES**

#### **A6–2.4.1 Guidelines for Management of Adverse Events Associated with Lurbinectedin**

##### **A6–2.4.1.1 Management of Hematological Abnormalities**

Regular monitoring of hematological tests, including differential WBC counts will be performed prior to each dose administration and in addition, on Day 10 of Cycle 1 and Cycle 2 (see the schedule of activities in Section 1.3, Table 2) in order to allow re-treatment of participants with lurbinectedin.

Participants with hematologic toxicities may require additional or more frequent laboratory tests according to institutional guidelines. The administration of a new cycle of lurbinectedin should be delayed until the participant's blood counts have reached adequate levels. [Table A6-3](#) provides treatment guidelines for severe cases of neutropenia and thrombocytopenia deemed related to lurbinectedin.

Dose adjustment, if applicable, should always be considered in participants who experience febrile neutropenia, neutropenic infection, sepsis or Grade 4 neutropenia or thrombocytopenia in prior cycles. Supportive care for thrombocytopenia or anemia, such as transfusions, may be managed according to institutional guidelines.

Extensive early antibiotic coverage and all available supportive measures as indicated should be applied during a febrile neutropenia episode or Grade 4 neutropenia with clinical or epidemiological signs of infection after lurbinectedin treatment.

Conversely, the presence of fever or signs of infection during the second week after lurbinectedin treatment start (usually from Days 8–18) must always motivate a thorough clinical examination and complete blood counts, including differential WBC counts.

No increase in opportunistic infections associated with lymphopenia or prolonged Grade 4 neutropenia (more than 2 weeks) has been described in trial participants with solid tumors, although no specific conclusions may be drawn due to the lack of randomized data. Nevertheless, no prophylactic antibiotic coverage is indicated at current available clinical guidelines/recommendations.

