**Table A6-3 Lurbinectedin Management Guidelines for Hematological Abnormalities**

Event	Management
Grade 1, 2 or 3 neutropenia or Grade 1, 2 or 3 thrombocytopenia without bleeding	

Manage according to institutional practice.

Continue lurbinectedin when ANC is <math>\geq 1.5 \times 10^9/L</math> for participants of non-African descent or <math>\geq 1.3 \times 10^9/L</math> for participants of African descent and when platelets are <math>\geq 100 \times 10^9/L</math>.

Neutropenia Grade 4 or any grade of febrile neutropenia	

Interrupt lurbinectedin.

Restart lurbinectedin, at reduced dose, when ANC <math>\geq 1.5 \times 10^9/L</math> for non-African descent or ANC <math>\geq 1.3 \times 10^9/L</math> for African descent and resolution of any infections.

Thrombocytopenia Grade 3 with bleeding or Grade 4	

Interrupt lurbinectedin until platelet count <math>\geq 100 \times 10^9/L</math> (100,000/<math>\mu</math>L) and resolution of any bleeding.

Restart lurbinectedin at reduced dose.

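### Appendix 6 gives inconsistent hematologic triggers for restarting lurbinectedin at a reduced dose, affecting Grade 3 thrombocytopenia with minor bleeding and non-febrile neutropenic infection

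*Protocol*

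**What the plan says.** Protocol Section 6.5 and A6-2.1 allow up to two lurbinectedin reductions. Section 6.5 refers to Table A6-1, which gives dose levels but no triggers. The triggers appear in three places in Appendix 6.

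- **A6-2.1 (Dose Modifications).** Participants may go on with lurbinectedin "at a reduced dose after they have adequately recovered from any of the following". The hematologic entries are "Grade 4 thrombocytopenia or Grade 3 thrombocytopenia concomitantly with Grade" ≥3 bleeding, and "Grade 4 neutropenia, any Grade febrile neutropenia or neutropenia associated with infection/sepsis". Separate entries cover treatment-related non-hematological toxicity of Grade ≥3, and dose delays that are frequent or longer than one week.
- **A6-2.4.1.1 (text introducing Table A6-3).** "Dose adjustment, if applicable, should always be considered in participants who experience febrile neutropenia, neutropenic infection, sepsis or Grade 4 neutropenia", the sentence then adding thrombocytopenia.
- **Table A6-3.** For "Neutropenia Grade 4 or any grade of febrile neutropenia" the action is to interrupt and then "Restart lurbinectedin, at reduced dose" once counts recover and infection clears. For "Thrombocytopenia Grade 3 with bleeding or Grade 4" it is also to interrupt and restart at a reduced dose. The remaining row, "Grade 1, 2 or 3 neutropenia or Grade 1, 2 or 3 thrombocytopenia without bleeding", is left to institutional practice, with lurbinectedin continuing once ANC and platelets reach set levels. That row mentions no dose change.

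**The concern.** A site treating a participant after hematologic toxicity needs one answer on the restart dose. For two kinds of event the answer depends on which part of Appendix 6 is open, and the mismatch runs in both directions: the table is wider for bleeding, and A6-2.1 is wider for infection. Neither list can simply be taken as the stricter one.

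The stakes come from how reductions work. A6-2.1 rules out re-escalation under any circumstances, caps reductions at two, and requires permanent discontinuation when a participant at 2 mg/m² has a toxicity that would warrant a further reduction. At the lowest level the trigger list is therefore also a stopping rule. Protocol Section 4.3.5 itself treats dose intensity as important to lurbinectedin's effect. The SAP plans summaries of dose intensity (4.5.1), of adverse events leading to interruption or modification (4.3.5) and of major protocol deviations (4.6.1). All of these are harder to interpret if sites applied different triggers.

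**Working it through.** There is no statistical figure to reproduce. The check sets the three places side by side, event by event.

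| Event | A6-2.1 | A6-2.4.1.1 text | Table A6-3 |
|---|---|---|---|
| Grade 4 thrombocytopenia | listed for reduced dose | adjustment considered | restart reduced |
| Grade 3 thrombocytopenia, bleeding Grade ≥3 | listed | not named | restart reduced |
| **Grade 3 thrombocytopenia, bleeding Grade 1–2** | **not listed** | **not named** | **restart reduced** |
| Grade 4 neutropenia | listed | adjustment considered | restart reduced |
| Febrile neutropenia, any grade | listed | adjustment considered | restart reduced |
| **Grade 1–3 neutropenia, infection, no fever** | **listed** | **adjustment considered** | **institutional practice, continue on ANC recovery, no reduction stated** |

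Step 1. A6-2.1 and Table A6-3 agree on four of the six rows and differ on the two in bold.

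Step 2. In the first bold row, the table excludes the event from its no-reduction row, because bleeding is present, and sends it to the reduced-dose row. A6-2.1 sets a bleeding threshold that the event does not meet.

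Step 3. In the second bold row, A6-2.1 puts no grade limit on neutropenia with infection or sepsis. The table's first row takes in all Grade 1–3 neutropenia with no exception for infection, and only fever or Grade 4 moves the event to the reduced-dose row.

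Step 4. The strength of wording differs as well. For febrile neutropenia and Grade 4 neutropenia or thrombocytopenia, the A6-2.4.1.1 text asks only for consideration, while the table it introduces directs a reduced dose.

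Step 5. Does anything settle it? Table A6-2 requires active infection and bleeding of any grade to be absent before re-treatment. That governs when treatment resumes, not the dose. No statement that one list prevails was found.

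Step 6. Size of one disputed reduction, from the levels in Table A6-1:

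- First reduction: 2.6 / 3.2 = 0.8125, which is 18.75% below the starting dose.
- Second reduction: 2.0 / 3.2 = 0.625, which is 37.5% below the starting dose.
- Beyond that: permanent discontinuation of lurbinectedin.

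**The case against.** The strongest reply is that the passages can be read together. A reader might infer that they give opposite orders, one reducing and one forbidding a reduction. The text does not go that far. A6-2.1 is permissive in form and silent on Grade 3 thrombocytopenia with lesser bleeding. Its paragraph of exceptions, which names events after which the same dose may continue, does not include that event, so a site following the table breaches nothing express in A6-2.1. The table's row for Grade 1–3 neutropenia defers to institutional practice, which could itself include a reduction. The A6-2.4.1.1 text names neutropenic infection and so leans the same way as A6-2.1.

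The gap is also narrower than the two bold rows suggest. If the infection or bleed is itself a treatment-related non-hematological toxicity of Grade ≥3, or the event causes frequent or more than one week's delay, A6-2.1 lists it on that ground. Waiting for infection or bleeding to clear under Table A6-2 makes such delay more likely.

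Finally, the Version 8 rationale says the clinical cut-off for the final OS analysis has been reached, so new wording cannot alter the dosing behind that result.

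All of this stands, and it limits the point to an inconsistency. It does not remove it. Low-grade infection or bleeding that clears without prolonged delay still gets a different answer from each place, and a site cannot tell which one governs.

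**Conclusion.** The point holds as an inconsistency in the reduced-dose triggers, confined to two situations plus a difference in strength of wording. It should be corrected. Its practical reach is participants still receiving lurbinectedin and the interpretation of dose modifications already made. For one participant, the difference is a dose 18.75% or 37.5% below the starting level, or the end of lurbinectedin.

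Two stronger readings are tempting and not supported.

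- A reader might scale event rates to the arm size to count those affected. Section 2.2.3 reports infection with Grade 3–4 neutropenia in 8.6%, and Grade ≥3 thrombocytopenia in 6.7%, of the SCLC cohort of Study B-005; A6-1.1.1 gives 9.7% for Grade 3/4 thrombocytopenia across Phase II and III studies. The first rate leaves out Grade 1–2 neutropenia, which A6-2.1 covers, and does not separate febrile or Grade 4 cases, where A6-2.1 and Table A6-3 agree. The platelet rates include Grade 4 and give no bleeding fraction. All come from single-agent use, whereas here lurbinectedin is given with atezolizumab after four induction cycles. They bound the affected number neither above nor below.
- A reader might infer that the primary comparison is compromised. No alpha, power or event count depends on these passages, and both primary estimands handle early discontinuation of study treatment by a treatment policy strategy.

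The conclusion assumes the ordinary reading that bleeding without a stated grade means any grade, and that the table row stating no reduction does not itself call for one.

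**What to change.** Reconcile A6-2.1, the A6-2.4.1.1 text and Table A6-3 to one set of hematologic triggers. The result needs one bleeding threshold for Grade 3 thrombocytopenia, an explicit entry for neutropenia with infection but no fever, and one strength of wording throughout, so that an event is not directed to a reduced dose in one place and merely considered for adjustment in another. Which triggers stand, and how strongly they bind, is for the sponsor to decide; no view is offered here.

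The cost is wording in one bullet list, one sentence and one table, by amendment or site clarification. No new data or procedures are needed. When past lurbinectedin dose modifications are reported, a sentence should say that the triggers were not uniform across Appendix 6.

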**Table A6-1 Lorbinecetin Dose Reduction Levels**

Dose Reduction Schedule	Lorbinecetin Dose (mg/m  ) a
Starting dose	3.2
First reduction	2.6
Second reduction	2.0

a Dose rounded to the first decimal.

In case atezolizumab is discontinued due to immune-related severe adverse events, treatment with lorbinecetin may continue as a single agent. If immune toxicity re-occurs despite discontinuation of atezolizumab, the participant will also discontinue lorbinecetin.

Participants may continue with atezolizumab as a single agent in case of lorbinecetin discontinuation.

